### **Whether or not the child proceeds to care proceedings**

To answer research question 4, we will use a binary outcome measure indicating whether a child that enters pre-proceedings (under the PLO) continues to care proceedings within 16 weeks of the first pre-proceedings meeting. Our sample will include any child (aged 0-12 at the point of referral) that has been referred within the trial period, and then be further restricted to those that have started pre-proceedings within 18 months of the referral start date.

This outcome will measure whether Family Safeguarding reduces the rate of escalations following pre-proceedings. Family Safeguarding teams work intensively with families during pre-proceedings, and some families' main interaction with the team might occur only when the case gets to this stage. This measure will thus assess whether the impact of the programme on children at the edge of care is particularly strong.

### **Repeat referrals for domestic violence, mental health or substance misuse**

To answer research question 5, the outcome measure is a binary variable of whether or not a child that has previously been referred for parental substance misuse, domestic violence, or parental mental health has been re-referred to children's social care within 18 months of the initial referral start date. Our sample will be restricted to children aged 0-12 at the time of referral who have been referred within the trial period and whose initial assessment identified parental substance misuse, domestic violence, or parental mental health as factors identified at the end of assessment. Since these factors are only identified at assessment, our sample

---

 Note that this does not include cases that lead directly to a Multi Agency Risk Assessment Conference (MARAC).

is restricted to children whose referral has progressed to an assessment and where one of the factors identified at assessment includes one of the three factors defined above.

Since a key element of Family Safeguarding is the inclusion of specialist adult practitioners with domestic abuse, mental health and substance misuse expertise, this analysis will allow us to evaluate one of the main components of the Family Safeguarding programme more closely.

### **Unauthorised school absence rates**

To answer research question 6, the outcome measure is a continuous variable measuring the percentage of sessions missed by a child within our analytical sample due to unauthorised absence, out of all sessions the child was expected to attend. We will measure the school attendance rate of three consecutive school terms, beginning with the closest school term beginning after the start of the period in which the child entered our sample. This will involve having up to three measurements per young person.

Unauthorised school absence rates are a valuable addition to the children's social care outcome measures detailed above as they directly relate to children's opportunities and outcomes outside of children's social care. Since there exists no direct link in the logic model between the model and unauthorised school absence rates, this outcome is of an exploratory nature to see whether we can capture part of the potential wider benefits of Family Safeguarding.

Care should be taken in the interpretation of the results of our analysis. Each result (pertaining to a specific outcome measure) will help create a picture of the changes that are taking place because of the intervention. However, in isolation we should be wary of concluding strongly that one direction is good or bad. This is especially true in terms of our measures relating to research questions 2 and 3. For example, a reduction in the length of CPPs could be positive - indicating that children's social care interventions address the families needs more rapidly. However, it could also be negative - and indicative instead of cases being closed prematurely, with families having unmet needs which could lead them to return to statutory services shortly after closing the case. Thus we will evaluate each analysis in the context of the others that we conduct. We will also interpret the results alongside the findings of the associated implementation and process evaluation, which may shed further light on the factors driving these outcome changes. We will also reflect any remaining ambiguity accordingly in our reports.

### **Sample size / MDES calculations**

*NB: These power calculations were conducted with the 'steppedwedge' package in Stata. We will conduct simulations to ensure the accuracy of these and update the trial protocol before any outcome data is collected. This could lead to changes in the minimum detectable effect size (MDES).*

---

 Note that the cases do not need to be open after assessment, i.e. we expand the population of interest beyond our analytical sample for this outcome measure.

	Proportion of children who become CLA within 18 months of referral start date
MDES	0.0105
Baseline measures	0.06
Intraclass correlation (ICC) Local authority	0.00722
Alpha	0.05
Power	0.8
One-sided or two-sided?	Two-sided
Level of intervention clustering	Local authority
Number of clusters	5
Average cluster size (children per local authority across all time periods)	10,200
Average cluster cell size (children per local authority per time period)	1,700
Sample Size (children) Total	51,000

We are powered to detect an effect size of 0.0105, or a 1.05 percentage point decrease or increase in the proportion of children who become looked after within 18 months of referral start date.

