## Design

The study design of the impact evaluation is a cross-sectional stepped-wedge cluster randomised controlled trial, where the timing of implementation is staggered across local authorities. The point at which local authorities begin implementing the intervention is selected at random, constrained by their level of readiness to implement the model. In this way, all the local authorities in the sample will eventually implement the Family Safeguarding model, but randomising the start date of the implementation of Family Safeguarding will allow service users in the local authorities that have not yet implemented the programme to act as a control group against service in local authorities where Family Safeguarding has already been implemented.

Given that, prior to the evaluation, there was already an existing need to stagger roll-outs over time, this means that nobody will be denied a service that they might otherwise have received. Local authorities implementing on different timescales will also allow us to take time-based effects into account, with every local authority also acting as a control group for itself over time.

RCT Design Table		
Trial type and number of arms		Stepped wedge cluster randomised controlled trial, two arms
Unit of randomisation		Local authority
Stratification variables		Low/High readiness to implement
Primary outcome	variable	Whether or not the child has become looked after
	measure	Coded 1 if the child has become looked after at any point within 18 months of the referral. Coded 0 if the child has not become looked after within this period.
	sample	Children aged 0-12 that have been referred within the trial period.

Secondary outcome 1	variable	Whether or not the child has returned to statutory services, following a CPP
	measure	Coded 1 if the child finishes a CPP and then returns to statutory services (i.e. begins a new CPP, CIN plan or becomes CLA) within 36 months of the referral start date, coded 0 if they have not re-entered statutory services within this time period.
	sample	Children aged 0-12 that have been referred within the trial period without them going into care.
Secondary outcome 2	variable	CPP plan duration
	measure	Discrete variable equal to the number of days that the child has been on a single CPP. Plan length is recorded up to 24 months from the start of the CPP and censored for larger values.

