### ***Sample size and cluster size***

The sample size was derived from the estimated baseline population for our primary outcome, which is the number of children who have been referred in a six month period. We take the average across local authorities that form part of our sample to calculate the average cluster size. The sample size is derived from the average cluster size times the number of local authorities in the trial and the six periods of the stepped-wedge implementation.

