## Appendix B: Power calculations Stata code

```
steppedwedge, binomial detectabledifference complete(1) vartotal(0) p1(0.06) m(1700) k(1)  
rho(0.00722) alpha(0.05) beta(0.8) steps(5)
```

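### The single 1.05-point MDES for a decrease or an increase rests on the baseline variance in both arms; allowing for the treated proportion gives about 1.0 point down and 1.1 points up, a minor correction

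*Protocol*

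**What the plan says.** The table under Sample size / MDES calculations gives an MDES of 0.0105, a baseline of 0.06, an ICC of 0.00722, alpha 0.05, power 0.8, a two-sided test, five clusters, 1,700 children per authority per period and 51,000 in total. The text below it reads "We are powered to detect an effect size of 0.0105", and continues "or a 1.05 percentage point decrease or increase in the proportion of children who become looked after". Both directions are therefore claimed in words.

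Appendix B gives the command: "steppedwedge, binomial detectabledifference complete(1) vartotal(0) p1(0.06) m(1700) k(1", followed by "rho(0.00722) alpha(0.05) beta(0.8) steps(5". It enters one proportion, the baseline, and no second one.

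The total comes from the "average cluster size times the number of local authorities in the trial and the six periods of the stepped-wedge implementation", and the Design section calls the study a "cross-sectional stepped-wedge cluster randomised controlled trial". The sample size section also marks the calculation as provisional: "We will conduct simulations to ensure the accuracy of these and update the trial protocol before any outcome data is collected".

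**The concern.** For a binary outcome the sampling variance depends on the proportion. If Family Safeguarding moves care entry away from 6%, the treated cells no longer have the baseline variance. It is smaller if care entry falls to 4.95% and larger if it rises to 7.05%. One symmetric MDES cannot then hold exactly in both directions, yet the protocol states one.

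What is at stake is how accurately the design's sensitivity is described. The primary outcome is tested two-sided, and the Risks section describes the model as being in equipoise, so a reader may take the 80% to apply equally to a rise and a fall of 1.05 points.

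**Working it through.** **Inputs, all from the sample size section and Appendix B.** Authorities I = 5; periods T = 6; m = 1,700 per cell (5 x 6 x 1,700 = 51,000); baseline p1 = 0.06; ICC = 0.00722; two-sided alpha 0.05; power 0.80. The multiplier is 1.960 + 0.842 = 2.802.

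**Step 1: reproduce the protocol's figure.** Use the standard (Hussey-Hughes) variance for a complete cross-sectional stepped wedge, with a random authority intercept and fixed period effects. Apply the baseline variance in every cell.

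- Total variance: 0.06 x 0.94 = 0.0564.
- Between-authority variance: t2 = 0.00722 x 0.0564 = 0.0004072.
- Cell-mean variance: s2 = (1 - 0.00722) x 0.0564 / 1,700 = 0.00003294.
- Design sums, one authority crossing at each step: U = 15 treated cells; W = 55 (sum of squared column totals); V = 55 (sum of squared row totals).
- Var = I s2 (s2 + T t2) / [(IU - W) s2 + (U^2 + ITU - TW - IV) t2] = 5 s2 (s2 + 6 t2) / (20 s2 + 70 t2) = 0.00001398.
- SE = 0.003739; MDES = 2.802 x 0.003739 = 0.01048; power at 0.0105 = 80.2%.

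Treating 0.0564 as the within-authority variance instead gives 0.01051 and 79.9%. Either way the printed 0.0105 is recovered. That the software applied the baseline variance to treated cells is inferred from this match and from the command containing only p1.

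**Step 2: let treated cells have their own variance.** The design, the ICC and t2 (kept at its baseline value) are unchanged. Only the binomial variance in treated cells changes, and the effect is estimated by generalised least squares.

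- Decrease: 0.0495 x 0.9505 = 0.0471. Increase: 0.0705 x 0.9295 = 0.0655. Baseline: 0.0564.

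| True change | SE | Effect/SE - 1.960 | Power | 80% MDES in that direction |
|---|---|---|---|---|
| -1.05 points | 0.003575 | 0.977 | 83.6% | 1.004 points |
| +1.05 points | 0.003881 | 0.745 | 77.2% | 1.089 points |

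Other ways of handling the variance agree closely. The average of the two arms, or the variance at the mean proportion, gives 83.4-83.5% and 77.0-77.1%, with an MDES of about 1.005 and 1.091 points.

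**Step 3: check the scale of the planned model.** The primary analysis is a logistic mixed model. With information m p (1 - p) per cell, and authority and period effects in the model:

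- Decrease: log odds ratio -0.2035, SE 0.0700, power 82.9%, MDES 1.013 points.
- Increase: log odds ratio +0.1725, SE 0.0644, power 76.4%, MDES 1.100 points.

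The asymmetry is therefore not a product of the risk-difference scale. On neither scale does a direction-specific MDES round to 1.05.

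**Step 4: compare with the roughness of the inputs.** Using the Step 1 method, a baseline anywhere in 0.055 to 0.065, all of which rounds to 0.06, gives an MDES of 1.006 to 1.087 points and power of 83.3% to 77.2%. A cell size of 1,575 instead of 1,700 gives 1.088 points and 77.1%.

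**The case against.** The best defence is that this is a planning convention and not a wrong sum. A common variance at the baseline proportion is a normal approximation. The command is published, the figure reproduces, and it lies between the two directional values. The asymmetry is no larger than the rounding of the baseline to 0.06. The cell size is itself called rough in the footnote on sample size (annual referrals halved, then multiplied by two thirds). The protocol says simulations will follow, and simulating a binary outcome brings in arm-specific variance automatically.

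Most of this stands, and it is why the point is minor. Two parts do not. Rough inputs shift the MDES for both directions together, so they do not make one figure right for both. And the simulation commitment does not say that both directions will be run; simulating a decrease alone would leave the sentence about an increase unchecked.

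A reader might go further and infer that the trial is unable to detect harm, or that a non-significant increase will be misread. The document does not support that. It does not say that power is equal in the two directions. It contains no harm test, stopping rule or interpretation tied to 80% power, and significance is judged at 5% whatever the planned power. The stated goal is to reduce the number of children looked after, and in that direction the printed figure is conservative.

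**Conclusion.** The point holds as a minor correction. The claim of 80% power at 1.05 points is not quite met for an increase (about 77%, or 76% on the log-odds scale) and is exceeded for a decrease (about 83-84%). The corresponding 80% MDES is about 1.09-1.10 points up and 1.00-1.01 points down, a shift of about 0.04-0.05 points either way.

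These figures rest on the protocol's own inputs, equal cell sizes, a constant within-authority correlation, and the same normal approximation. Like the printed 0.0105, they make no allowance for having only five clusters, so they correct the asymmetry and nothing else. No design decision turns on the difference.

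**What to change.** In the sample size section, replace the symmetric sentence with direction-specific figures: 80% power for a decrease of about 1.0 point or an increase of about 1.1 points. Alternatively, keep 1.05 points and limit the claim to a decrease. Add that the figures rely on a normal approximation with five clusters. Specify that the simulations already promised will be run for a decrease and for an increase, under the logit model planned for the primary analysis.

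The cost is one restated line and a second simulation scenario in an update the protocol already commits to make before outcome data are collected. Sample size, design and analysis do not change.

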### ***Sample size and cluster size***

The sample size was derived from the estimated baseline population for our primary outcome, which is the number of children who have been referred in a six month period. We take the average across local authorities that form part of our sample to calculate the average cluster size. The sample size is derived from the average cluster size times the number of local authorities in the trial and the six periods of the stepped-wedge implementation.

### ***Baseline rates***

Baseline rates were calculated by averaging the share of children who became looked after in a given year out of the number of referrals in the year across local authorities who are part of our sample. Data was sourced from the Local Authority Interactive Tool (LAIT).

### ***Intra-cluster correlation***

We use the latest available historical data to estimate the intra-cluster correlation (ICC). Using a proxy for the sample size and baseline rates as above (taking into account the

---

 Using publicly available data, we used the number of referrals within a year. Figures were divided by 2 to derive an estimate of the cluster size for our 6-month intervals and multiplied with 2/3 to arrive at a rough estimate for our age group of interest.

 <https://www.gov.uk/government/publications/local-authority-interactive-tool-lait>

different sample sizes and baseline rates in each individual local authority), we can calculate the ICC using the `loneway` command in Stata. Since our outcome is binary, we do not need any additional individual-level information to calculate the ICC.

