## Conditions

Children that form part of the samples described above will be designated as part of the treatment and control groups according to whether Family Safeguarding was implemented in their local authority at the time of their first referral start date in the trial period. This date also marks the starting point from which we measure any outcomes over the periods of time defined in the RCT Design Table above. Compared to other possible dates at a later stage in the referral, this constitutes a conservative approach. Some children in the control group might have been in contact with Family Safeguarding teams at a later stage of their referral which can bias our estimate downwards. We revisit this approach in our sensitivity analysis.

We only consider referrals that started during or after our baseline period and do not allow children to enter our sample twice i.e. any additional referrals after the first referral in the trial period defining our baseline population will not lead to additional entry into the sample, though the consequences of subsequent referrals may affect the outcome coding.

For Secondary Outcome 5 - Repeat referrals for domestic violence, mental health or substance misuse - we alter our definition of treatment and control. Here, the relevant referral date will be the first referral in the trial period, where the following assessment identified one of the three factors at the end of assessment. This is because some activities of Family Safeguarding such as specialist adult practitioners only focus on children in this subgroup. Thus, any referrals prior to this, where the assessment following a referral did not identify one of these factors at the end of assessment, will be disregarded.

Conditions Table		
Condition	Primary Outcome and Secondary Outcomes 1-4 & 6 definition	Secondary Outcome 5 definition
Control	Children whose first referral in the trial period took place when the local authority was running their business as usual model.	Children whose first referral in the trial period - where the factors identified at the end of assessment included either parental substance misuse, parental mental health, or domestic violence - took place when the local authority was running their business as usual model.

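### The sample size, the 6% baseline and the 1.05 pp MDES are built on referral counts, but each child is analysed once, so the stated absolute MDES is too favourable by an unknown amount

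*Protocol*

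**What the plan says.** Under Sample size and cluster size, the basis of the calculation is described as the baseline population for the primary outcome, "which is the number of children who have been referred in a six month period". The total is then built up: "The sample size is derived from the average cluster size times the number of local authorities in the trial and the six periods". The table under Sample size / MDES calculations labels 1,700, 10,200 and 51,000 as children, and the front page repeats 51,000.

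Footnote 8, which belongs to that section but is printed under Intra-cluster correlation, gives the source: "Using publicly available data, we used the number of referrals within a year". It makes two adjustments, division by 2 for a half-year and multiplication by 2/3 for age. Baseline rates describes the 6% as an average over authorities of "the share of children who became looked after in a given year out of the number of referrals in the year". Intra-cluster correlation derives 0.00722 from the same proxies.

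The cohort is defined differently. Under Conditions, the investigators "do not allow children to enter our sample twice", and footnote 12 repeats this. The RCT Design Table measures care entry within 18 months of referral in children aged 0-12. The stated result is: "We are powered to detect an effect size of 0.0105, or a 1.05 percentage point decrease or increase".

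**The concern.** A referral and a child are different units whenever a child is referred more than once. The protocol expects this to happen. Conditions provides for further referrals after the first, and re-referral within 18 months is secondary outcome 5. Counting only first referrals over six half-year periods removes every later referral of the same child, whether it falls in the same period or a later one. Halving an annual count removes none of them.

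The same unit enters N, the baseline rate and, through the proxies, the ICC. With five clusters, readers of a null result will lean on the stated MDES to judge what effect the trial could have missed. If that figure describes referrals and not the analysed children, it gives too favourable an answer in percentage points.

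**Working it through.** **Inputs (MDES table and Appendix B).** Baseline p = 0.06; cell size m = 1,700; ICC ρ = 0.00722; two-sided α = 0.05; power 0.80; I = 5 authorities, one per step; T = 6 periods.

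**Reproducing the plan.** N = 1,700 × 5 × 6 = 51,000 exactly, so nothing was taken out for repeats.

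For the MDES, use the Hussey–Hughes variance for a complete stepped wedge:

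Var = I·s²(s² + T·τ²) / [(I·U − W)s² + (U² + I·T·U − T·W − I·V)τ²]

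- τ² = ρ·p(1−p) = 0.00722 × 0.0564 = 0.0004072
- s² = (1−ρ)·p(1−p)/m = 0.99278 × 0.0564 / 1,700 = 0.00003294
- U = 15, W = 55 and V = 55 for this layout, so I·U − W = 20 and the τ² coefficient is 225 + 450 − 330 − 275 = 70

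This gives Var = 0.00001398 and SE = 0.003739. MDES = (1.960 + 0.842) × 0.003739 = 0.01048, which is the stated 0.0105.

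**Changing the unit.** Let f be the share of referrals that are a child's first in the trial period. The protocol does not give f, so the values below are assumptions. N becomes 51,000·f and m becomes 1,700·f. Care entries already count children, so only the denominator changes and the rate becomes 0.06/f. The number of care entries stays at 51,000 × 0.06 = 3,060. The ICC is held at 0.00722. Power for 1.05 pp = Φ(0.0105/SE − 1.96).

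| f (assumed) | N | MDES, baseline 6% | Per-child baseline | MDES, rescaled | Power for 1.05 pp, rescaled | Rescaled MDES / baseline |
|---|---|---|---|---|---|---|
| 1.00 | 51,000 | 1.05 pp | 6.0% | 1.05 pp | 80% | 17.5% |
| 0.95 | 48,450 | 1.07 pp | 6.3% | 1.10 pp | 76% | 17.4% |
| 0.90 | 45,900 | 1.10 pp | 6.7% | 1.16 pp | 72% | 17.4% |
| 0.80 | 40,800 | 1.17 pp | 7.5% | 1.30 pp | 62% | 17.3% |
| 0.70 | 35,700 | 1.25 pp | 8.6% | 1.47 pp | 51% | 17.2% |

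The rescaled columns are the consistent ones, because the referral denominator affects N and the rate together. The column at 6% corrects N alone.

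**Uneven periods.** First-entry counting thins the later periods. An assumed declining profile (1, 0.9, 0.85, 0.8, 0.78 and 0.75 of 1,700; total 43,180) gives 1.14 pp at a 6% baseline. A flat f = 0.85 (43,350) also gives 1.14 pp. For that profile the total matters more than its shape.

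**A separate mismatch in the baseline.** Baseline rates uses a one-year ratio and states no age restriction, while the outcome is an 18-month risk at ages 0-12. This is independent of the referral unit and is not in the table.

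**The case against.** The strongest reply is that power is not lost on the scale closest to the model. The primary analysis is logistic. Care entries number 3,060 at any f, and with N and the rate both rescaled the relative MDES moves only from 17.5% to 17.2% at f = 0.70. That stands, and it limits the point to the absolute scale. The protocol makes its claim on that scale.

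It is also fair that the protocol calls its inputs a proxy and a rough estimate, and promises simulations that may change the MDES. The word rough is attached to the age factor, however, and nowhere is the change of unit acknowledged. The simulations are promised to check the accuracy of the calculation. A reader might infer that they will carry the same inputs forward, but the text does not say which inputs they will use.

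Three other stronger readings are not supported. One might conclude that 51,000 cannot be reached. The 2/3 age factor and past referral volumes could err in either direction, so the shortfall follows only with those held. One might take the 6% to cover all ages, but the section states no age range either way. One might quote power of 71% or 65% at f = 0.80 or 0.70, but those figures correct N and leave the rate per referral, which mixes units.

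Finally, the five authorities, the dates and the eligibility rule determine enrolment, so no recruitment target is missed. That stands too.

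**Conclusion.** The mismatch of units is established from the text: referrals in the planning inputs, first-referred children in the cohort, and no step between them. Neither 1,700 × 5 × 6 nor 0.0105 is an arithmetic error. Other inputs held, the direction is certain for any f below 1: fewer than 51,000 distinct children, a per-child rate above 6% from the unit alone, and an absolute MDES above 1.05 pp at 80% power.

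The size is not known. It depends on a repeat share that the protocol does not give. With the baseline rescaled and the ICC fixed, the range runs from slight (1.10 pp and 76% power at f = 0.95) to substantial (1.47 pp and 51% at f = 0.70). The ability to detect a given proportionate change of about 17% is essentially unchanged. The one-year window and unstated age range of the baseline are a further reason to re-estimate it, with an effect not quantified here.

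**What to change.** Use the update that Sample size / MDES calculations already promises before outcome data are collected. From past local authority records, count distinct children aged 0-12 at their first referral in a 36-month window, by half-year, with their 18-month care-entry rate. Re-run the calculation with those six cell sizes, that rate and an ICC estimated on the same basis. Restate 51,000 (front page and MDES table), 0.06, 0.00722 and 0.0105, and give the MDES in percentage points and relative to baseline.

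If the records cannot be had, label 51,000 as referral-based and show the MDES over a stated range of repeat shares, as in the table above.

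The cost is a modest de-duplicated data request with linked 18-month outcomes, and a less favourable absolute MDES. Enrolment is unchanged.
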